7. RISK MANAGEMENT

Restore is a low risk trial. Any of the risks encountered by the participant are those associated with surgery for the treatment of fecal incontinence or LARS. In the event that readmissions or SNS lead removals are high, the study will be terminated as described in the previous section. We feel that any risk associated with participation in *Restore* is minimal and will be offset by improved patient reported outcomes. The knowledge obtained by the study personnel regarding the feasibility of sacral nerve stimulation for the treatment of fecal incontinence and LARS in association with colorectal cancer will be used to assess the potential of expanded cohorts as previously described. Adverse events (AE), \geq grade 3, using CTCAE v. 4 and serious adverse events (SAE) related to the procedure that occur within 30 days after will be reported. Reportable AE and SAE would include, but are not limited to, lead migration, wound infection, pneumonia, intractable pain related to surgical complications such as wound infection, unplanned or unanticipated readmission within 30 days, stroke, myocardial infarction, perioperative cardiovascular events, readmission if it is related to the SNS procedure, SNS lead removal due to any reason other than failure, or perioperative death due to surgery or complications.

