Visit 2 (Sacral Nerve Stimulator Lead Placement): Surgery for stage 1 sacral nerve stimulator placement will occur within 30 days after enrollment in the study. The patient will arrive at the pre-operative holding areas at UTMDACC's main campus for their outpatient surgery. The representative for the implantable SNS company (Medtronic) will be present at the operation for assistance with placement of the leads per standard of care and for assistance with patient education following lead placement. The patients are sent home with a diary to record daily bowel and bladder habits during the interval period.

Visit 3 (Assessment of Symptoms and Battery Implantation or Lead Removal): Surgery for stage 2 sacral nerve stimulator battery implantation or lead removal will occur around 2 weeks (+7 days) after SNS placement. The patient will arrive to the holding area with their post-implantation bowel and bladder habit diary from visit 2. Review of the bowel diary information and a review of symptoms from visit 1 and visit 2 with the patient will be completed and then a decision made to either implant the battery or remove the stimulator leads as per standard of care. If the bowel diary reveals $\geq 50\%$ decrease in FI or LARS symptoms between visit 1 and visit 2, the external temporary battery will be replaced with an implantable battery. If the bowel diary reveals $< 50\%$ decrease in FI or LARS symptoms, the previously placed leads and external battery will be evaluated for proper positioning and functioning in the OR and removed if they remain properly positioned. Following the procedure, the patient is discharged home. If the device is removed, their participation in the study is complete, but data collected to this point will still be used in study analysis and reporting.

Visit 4 (Post-operative Assessment): Post-operative evaluation. The patients return to clinic at 1 month (+/- 2 weeks) after completion of visit 3 for a wound evaluation, device check, and symptom review. At this point, the patients will complete study questionnaires (on paper, over the phone/teleconference system, or electronically through REDCap) and undergo a repeat ARM.

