Visits 5 (1-Year Follow Up) and 6 (3-Year Follow Up): Patients will return to clinic at 1 and 3 years (+/- 3 months) for evaluation, per routine standard of care, from their SNS battery for evaluation. Patients will again complete validated questionnaires (on paper, over the phone/teleconference system, or electronically through REDCap) at this visit. After collection of this data, their participation in this study is complete. If for any reason patients are not able to return to the clinic at these time points, study questionnaires may be filled out via mail or over the phone/teleconference system, or electronically through REDCap.

Table 1. Study Assessment Calendar

	Initial Evaluation/ Visit 1	Visit 2 (+ 4 weeks)	Visit 3 (+ 7 days)	Visit 4 (+/- 2 weeks)	Assessment at 1 and 3 years*
--	--------------------------------	------------------------	-----------------------	--------------------------	------------------------------

Physical exam + anorectal manometry + Post-void residual Bladder scan	X			X	
SNS Lead Placement		X			
Battery Implantation or Lead Removal			X		
FIQoL and FISI Instrument	X			X	X
MSKCC Bowel Function Instrument	X			X	X
LARS Score Questionnaire	X			X	X
EORTC QLQ-CR29	X			X	X
Cleveland Clinic Incontinence Score Instrument	X			X	X
EQ-5D-5L Instrument	X			X	X
ICSmaleSF or ICIS- FLUTS (as appropriate) Instrument	X			X	X
Bowel/Bladder Diary	X	X			
Adverse Events**			X		

* +/- 3 months

** See Section 7. Risk Management

Clinical Data Collection

Data regarding patients, tumors, treatments, and disease/vital status will be obtained from existing medical records. Patient data collected will include, but is not limited to: demographic information, lab values, comorbidities and medical history, medications, test results (i.e., EKG). Tumor data collected will include, but is not limited to: site, stage, histology, distance from anal verge, histologic grade, clinical TNM stage, method of clinical stage, tumor size, biomarker status (e.g., microsatellite status, KRAS, BRAF mutation status, etc.) as available. Treatment data for the primary cancer diagnosis will be collected including chemotherapy and radiation regimens as well as surgical procedures, complications and outcomes. Clinical data will be collected until the patient is taken off study.

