6.5. Interim Analyses

A Bayesian sequential monitoring design (Thall et al. 1995 and 1998)[27, 28] will be used to monitor the trial for response and adverse events. Interim assessments will be performed in groups of 6 patients, with accrual held for evaluation for each cohort until enough information is available to determine the outcome. Each patient cohort will be evaluated separately and will continue if patients are exhibiting reasonable adverse event rates and SNS response rates. If one cohort stops, the other cohort will continue according to the monitoring rules. Calculations were performed in MultcLean Desktop version 2.1.0.

Interim Analyses for Futility

A patient will be considered to have SNS success as defined above. The patient cohort will be stopped early if $\Pr[\theta_S < 0.50 | \text{data}] > 0.95$, where θ_S denotes the SNS success rate. That is, given the outcomes from the patients who have already been evaluated, if it is determined that there is a more than 95% chance that the response rate is less than 50% (constant), the arm will be stopped for futility. Assuming a prior distribution of θ_S for each experimental treatment of $\sim \text{beta}(1,1)$, pre-defined stopping boundaries corresponding to this probability criterion are provided in the following table.

If there are this many patients evaluable for SNS success	6	12	18	24	30*
Stop the cohort if there are this many or fewer SNS successes	0	3	5	7	10

* The cohort will stop at 30 regardless of the number of SNS successes, but if there are 10 or fewer, then the implant is not promising enough for future trials in this patient cohort.

Assuming the cohort does not stop for adverse events first, 6 patients will be accrued. If none of the 6 patients have SNS success, stop the cohort and the implant will be declared as ineffective for this population. Patients will continue to be enrolled on the other cohort as long as it is open. If there is at least 1 success, the next 6 patients will be entered in the cohort, unless they need to stop according to the adverse event boundaries below. Continue checking after every 6 patients for sufficient SNS success assuming the trial does not stop for adverse events first. The operating characteristics for efficacy and adverse events are summarized after the adverse event rules below.

Interim Analyses for Safety

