Under the same model described for SNS success, adverse events will be monitored assuming an *a priori* probability of limiting adverse events following Beta(0.6, 1.4) in the current patient cohort. Cohort limiting events (CLE) are defined as perioperative cardiovascular events, readmission if it is related to the SNS procedure, SNS lead removal due to any reason other than failure, or perioperative death due to surgery or complications. The patient cohort will be terminated if $\text{Prob}(\text{CLE} > 0.30 | \text{data}) > 0.95$. The specific rules for stopping after each cohort are included in the table here.

If there are this many patients (or more) with CLE	5	7	9	12	14
Stop the patient cohort if there are this many (or fewer) patients who are evaluable (have CLE, had battery implant without CLE, or had leads removed for failure without CLE.)	6	12	18	24	30*

* The cohort will stop at 30 patients, but if 14 or more patients have CLE, then the implant is too dangerous for this cohort.

Six patients will be accrued before the first analysis. If 5 or more of the 6 patients have CLE, stop the cohort and the implant will be declared as too dangerous for this population. If there are 4 or fewer CLEs, enroll the next 6 patients assuming the cohort didn't stop for futility.

The operating characteristics are summarized in the following table:

The operating characteristics for each patient cohort are shown in the following table.

		Stop if $\text{Prob}\{\theta_S < 0.50 \text{data}\} > 0.95$ or Stop if $\text{Prob}\{\text{CLE} > 0.30 \text{data}\} > 0.95$	
True	True	Pr(stop early)	Mean Number of Median

Adverse Event Rate	Response Rate		Patients	(25 th %ile, 75 th %ile)
0.1	0.30	0.68	18.5	12 (12, 30)
0.2	0.30	0.68	18.5	12 (12, 30)
0.3	0.30	0.71	18.0	12 (12, 30)
0.4	0.30	0.79	16.5	12 (12, 24)
0.5	0.30	0.90	14.0	12 (12, 18)
0.1	0.40	0.33	24.6	30 (18, 30)
0.2	0.40	0.33	24.5	30 (18, 30)
0.3	0.40	0.38	23.7	30 (12, 30)
0.4	0.40	0.55	21.0	18 (12, 30)
0.5	0.40	0.79	16.8	12 (12, 24)
0.1	0.50	0.10	28.3	30 (30, 30)
0.2	0.50	0.11	28.1	30 (30, 30)
0.3	0.50	0.18	27.1	30 (30, 30)
0.4	0.50	0.40	23.7	30 (18, 30)
0.5	0.50	0.72	18.4	18 (12, 30)
0.1	0.60	0.02	29.6	30 (30, 30)
0.2	0.60	0.03	29.5	30 (30, 30)
0.3	0.60	0.10	28.4	30 (30, 30)
0.4	0.60	0.34	24.7	30 (18, 30)
0.5	0.60	0.69	19.0	18 (12, 30)
0.1	0.70	0.003	30.0	30 (30, 30)
0.2	0.70	0.01	29.8	30 (30, 30)
0.3	0.70	0.08	28.7	30 (30, 30)
0.4	0.70	0.33	25.0	30 (18, 30)
0.5	0.70	0.68	19.1	18 (12, 30)

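### No safety data collection is planned after leads are removed for failure, so later cohort limiting events can be missed and the patient scored as event-free

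*Combined protocol and SAP*

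**What the plan says.** **Reporting window.** Section 7 covers adverse events of at least "grade 3, using CTCAE v. 4 and serious adverse events (SAE) related to the procedure that occur within 30 days after will be reported". It makes no exception for patients whose leads are removed, and its list of reportable events repeats all four CLE components.

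**End of participation.** Section 5 (Visit 3) states: "If the device is removed, their participation in the study is complete, but data collected to this point will still be used". The Visit 3 operation, battery implant or lead removal, "will occur around 2 weeks (+7 days) after SNS placement". Section 5 (Clinical Data Collection) adds: "Clinical data will be collected until the patient is taken off study". Implanted patients are seen again at Visit 4, one month (plus or minus two weeks) after Visit 3. Patients with removed leads are not.

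**Safety rule.** Section 6.5 defines CLEs as perioperative cardiovascular events, "readmission if it is related to the SNS procedure, SNS lead removal due to any reason other than failure", and perioperative death. No time window is given. Besides patients with a CLE, the evaluable set contains those who "had battery implant without CLE, or had leads removed for failure without CLE". At 30 patients, "if 14 or more patients have CLE, then the implant is too dangerous for this cohort". Interim looks come every 6 patients, "with accrual held for evaluation for each cohort until enough information is available to determine the outcome".

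**The concern.** Lead removal is itself a return to the operating room, after which the patient goes home. From that point the visit rules plan no safety collection, while Section 7 still promises a 30-day report. The two sections do not fit together for this group, and the safety rule fills the gap by default: with no recorded event, the patient enters the denominator as event-free, with the same weight as an implanted patient who returns at Visit 4.

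Missed events can only lower the CLE count, and the group exposed to this grows as SNS success falls. The count drives the safety stop, the final judgement at 30 patients and the CLE rate reported under Section 6.6. It matters most in the radiation only cohort. Section 6.1 says that cohort is there to establish safety, and Section 2 says no SNS data have been published for such patients.

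**Working it through.** **1. Days without planned collection.** With no lead repositioning, Visit 3 falls on day 14 to 21 after lead placement. Of a 30-day window from lead placement, 30 − 21 = 9 to 30 − 14 = 16 days remain. Of a 30-day window from the removal, everything after discharge remains.

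**2. Events that can still occur.** Three of the four CLE components can follow removal: SNS-related readmission, perioperative cardiovascular event and perioperative death. Lead removal for another reason cannot.

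**3. The plan's own figures.** With prior Beta(0.6, 1.4) and r CLEs in n patients, the rule stops when Pr(p > 0.30 | Beta(0.6 + r, 1.4 + n − r)) > 0.95. The smallest such r at n = 6, 12, 18, 24, 30 is 5, 7, 9, 12, 14, as in the plan. One event decides at a boundary: 7/12 gives 0.969 (stop) and 6/12 gives 0.905 (continue); 14/30 gives 0.967 and 13/30 gives 0.929.

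An exact recursion used looks at 6, 12, 18 and 24, futility limits 0, 3, 5, 7, safety limits 5, 7, 9, 12, and success independent of CLE. It reproduces all 25 operating-characteristic rows, with Pr(stop early) within 0.005 and mean N to 0.1. At success 0.50 and CLE 0.1 to 0.5 it gives 0.101, 0.108, 0.176, 0.397, 0.715 (plan: 0.10, 0.11, 0.18, 0.40, 0.72). The plan's table therefore corresponds to every CLE being seen.

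**4. Patients exposed, per 30 operated.** Implant rates in Section 2 are 79.1% overall and 47% at the lowest; 50% is the plan's benchmark.
- 30 × (1 − 0.791) = 6.3
- 30 × (1 − 0.50) = 15
- 30 × (1 − 0.47) = 15.9

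These are upper bounds at each rate. They treat every non-success as removed for failure, whereas some patients never have leads placed and removals for other reasons are already CLEs.

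**5. Undercount of the CLE rate.** Let s be the success rate, q the true CLE rate, and f the share of CLEs in non-successes that fall after removal and go unseen. The documents do not give f; 10%, 25% and 50% are assumptions. Observed rate = q × [1 − (1 − s)f], so the relative undercount is (1 − s)f.

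| s | f = 10% | f = 25% | f = 50% |
|---|---|---|---|
| 0.791 | 2.1% | 5.2% | 10.4% |
| 0.50 | 5% | 12.5% | 25% |
| 0.47 | 5.3% | 13.3% | 26.5% |

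**6. Effect on Pr(stop early)**, same recursion, futility and safety together:

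| s | q | f = 0 | 10% | 25% | 50% |
|---|---|---|---|---|---|
| 0.791 | 0.3 | 0.083 | 0.074 | 0.062 | 0.045 |
| 0.791 | 0.5 | 0.683 | 0.648 | 0.594 | 0.499 |
| 0.50 | 0.4 | 0.397 | 0.342 | 0.269 | 0.180 |
| 0.50 | 0.5 | 0.715 | 0.641 | 0.524 | 0.338 |

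At q = 0.2 and s = 0.50, stops for safety are below 1% at every f.

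**The case against.** A reader might infer that 30-day events cannot be collected in these patients, or that the two rules cannot both be followed. The documents do not support that. Section 7 applies to everyone, the calendar's adverse-event row refers to it, and Section 5 draws clinical data from existing medical records, so a 30-day report could be made without a visit. Events up to and during the removal are captured. Nor does the safety rule treat every failure as event-free: one with a recorded CLE counts as a CLE. The accrual hold could also be read as allowing a wait. These points narrow the matter to a gap after removal. They do not close it, because no section says who looks for events once participation has ended, and Section 5 restricts use to data already gathered.

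A reader might also take the fall from 0.72 to 0.34 as the expected loss in the stopping rule. It needs a true CLE rate of 0.5 and half of the CLEs in failures arriving late, so that 0.5 × 0.5 = 25% of failure patients have a first CLE after going home from removal. Nothing in the documents supports such a figure for a trial that Section 7 calls low risk. The 7-versus-6 example likewise needs 7/12 = 58% of patients with a CLE. This part of the objection stands.

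**Conclusion.** The point holds as a gap in planned follow-up and an inconsistency between Sections 5 and 7 that carries into the Section 6.5 safety rule. The direction of the bias is certain (downward); its size is not, because the documents give neither a CLE rate nor its timing. At true CLE rates of 0.2 or less the stopping rule is barely affected, and the harm is an understated CLE rate, by (1 − s)f in relative terms. At a true rate of 0.3 with 79.1% implanted, a 25% late share lowers Pr(stop early) only from 0.083 to 0.062. Large losses appear only at rates of 0.4 to 0.5 with a substantial late share. The plan's boundaries and operating characteristics are arithmetically correct. The change is worth making because it is cheap and the radiation only cohort has no outside data against which to check its count.

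**What to change.** - **Section 5, Visit 3:** state that a patient whose leads are removed stays on study for safety until 30 days after the removal, with one phone contact or chart check.
- **Sections 7 and 6.5:** state that the 30-day window for adverse events, serious adverse events and CLEs runs from each operation (lead placement, any repositioning, battery implant or lead removal). A CLE found in that window is added to the count at the next look and in the final CLE rate.

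Boundaries, prior and N do not change. The cost is at most about 6 to 16 brief contacts or chart checks per 30 operated patients. Holding accrual until every patient's window has closed is optional. If looks are now made at Visit 3, it would add up to 30 days at each of four interim looks, 4 × 30 = 120 days or about 4 months per cohort, and the core fix does not need it.

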8. DATA MANAGEMENT

The study team is committed to protecting patient confidentiality at all times and in all circumstances. No patient identifying information will be used in the publication of findings and all information extracted from the medical record will be entered onto coded data sheets which will be maintained on databases stored in approved locations and only accessible by delegated UTMDACC employees. All printable hard copies of study documents such as bladder and bowel diaries or other study related instruments, will be stored in a secured location on the UTMDACC campus. If needed, hard copies of the coded study data may also be stored in a locked cabinet in

the principal investigator's office. All electronic data will be entered and stored in an institutionally approved database (e.g., REDCap) on a secured UTMDACC server.

10. APPENDICES

- A. Combined Fecal Incontinence Quality of Life Questionnaire (FIQoL) and Fecal Incontinence Severity Index (FISI)
- B. Memorial Sloan-Kettering Cancer Center (MSKCC) Bowel Function Instrument
- C. Low Anterior Resection Syndrome (LARS) Score Bowel Function Questionnaire
- D. EuroQol Group EQ-5D-5L™ (EQ-5D-5L)
- E. Cleveland Clinic Incontinence Score (CCIS) Instrument
- F. International Consultation on Incontinence Questionnaire-Female Lower Urinary Tract Symptoms (ICIQ-FLUTS)
- G. International Continence Society Male Short Form (ICSmaleSF)
- H. Bladder Symptom Tracker (Medtronic) as part of the urinary diary
- I. Bowel Symptom Tracker (Medtronic) as part of the bowel diary
- J. EORTC QLQ – CR29®
- K. REDCap Survey Message and MyChart Survey Reminder
